### **4.2 Analysis Software**

The statistical analysis is performed using the SAS® statistical software package (Statistical Analysis System, Version 9.4 or later).

## **5. Data Preparation**

### **5.1 Data Handling and Medical Coding**

For data quality control, medical coding and data provided by third parties which is not contained in the clinical database (e.g. pharmacokinetic data, central reader data), please refer to the Data Management Plan (version 1.0, dated 11APR2024 or higher including the Data Validation Plan (version 3.0. dated 03JUL2024) or higher. The adverse event terms are coded using the Medical Dictionary for Regulatory Activities (MedDRA) thesaurus, Version, 26.0 (Mar 2023) (or higher).

### **5.2 CDISC**

All output as defined in the SAP are generated based on CDISC ADaM datasets, as per contract with Haleon. Specifications for the ADaM datasets (as well as SDTM datasets) are described in a separate document.

### 5.3 SAS-Programming Quality Level

The following quality level of programming deliverables is applied, as per contract with Haleon:  
All statistical output receives a tailored Quality Control (QC) approach by:

**Table 2: SAS-Programming Quality Level**

DELIVERABLE	DOUBLE PROGRAMMING?
CDISC SDTM datasets	
Including QC against the applicable CDISC guidelines.	YES
CDISC ADaM datasets	
Including QC against the SAP and applicable CDISC guidelines.	YES
Derived datasets	YES
Tables and Figures	YES
Inferential analyses	YES
Data Listings	
Listings	NO
Listings for Data Review Meeting that do not need complex selection	NO
Listings for Data Review Meeting that do need complex selection*	YES

\* The selection of the data is double programmed from the source dataset.

All TLFs undergo the following by the Quality Control (QC) team:

- Comparison with specifications (i.e., SAP and shells)
- Cross checking with other TLFs for consistency and correctness
- Sensibility review
- SAS log review

In addition, a Senior Review is also performed by a reviewer independent of the study team. The reviewer studies all tables, listings and graphs for consistency and correctness.

All TLFs undergo comparison with specification (i.e. SAP and templates), cross checking with other TLFs for consistency and correctness, a sensibility review, and SAS log review by the Lead Statistical Programmer or Lead Statistician.

## 6. Analysis Populations and Subgroups

### 6.1 Analysis Populations

#### Total Set (TOT)

The Total Set consists of all subjects who provided informed consent on the 'Informed Consent' Electronic Case Report form (eCRF) page.

#### Enrolled Population

The enrolled population will include all subjects who meet the inclusion/exclusion criteria as recorded on the 'Subject Eligibility: Inclusion/Exclusion Criteria' eCRF page.

#### Screening Failures

Screening Failures are defined as subjects who provided informed consent but failed to meet all inclusion criteria and/or met at least one exclusion criteria, as recorded on the 'Subject Eligibility: Inclusion/Exclusion Criteria' eCRF page.

#### Safety Population (SAF)

The safety population will include all subjects who use study product at least once i.e. if a subject has a date of first study treatment administration as described in section 7.1. The safety population will be used for safety variables.

#### Modified Intent-To-Treat (mITT) population

The modified Intent-To-Treat (mITT) population will include all subjects who meet the inclusion/exclusion criteria, who use study product at least once and have data from at least one post baseline QoL questionnaire to support at least one of the secondary endpoint assessments (i.e. have a non-missing response in the 'Western Ontario and McMaster University Osteoarthritis Index' or 'EQ-5D-5L Quality of Life Questionnaire' eDiary pages). The mITT population will be used for all efficacy analysis.

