### **13.2 Populations for Analysis**

- The enrolled population will include all subjects who meet the inclusion/exclusion criteria.
- The safety population will include all subjects who use study product at least once. Safety population will be used of safety variables.
- The modified Intent-To-Treat (mITT) population will include all subjects who use study product at least once and have data from at least one post baseline QoL questionnaire to support at least one of the secondary endpoint assessments. QoL and ePRO data will be summarized using the mITT population only.

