### **3.5 Changes in the Conduct of Study or Planned Analysis compared to protocol**

Protocol Version Final 4.0 dated 08JUL2024 states in Section 13.2 on page 55 that:

“The modified Intent-To-Treat (mITT) population will include all subjects who use study product at least once and have data from at least one post baseline QoL questionnaire to support at least one of the secondary endpoint assessments. QoL and ePRO data will be summarized using the mITT population only”.

This has been updated in the SAP to include that subjects must meet the inclusion/exclusion criteria to be included in the mITT as below:

“The modified Intent-To-Treat (mITT) population will include all subjects who meet the inclusion/exclusion criteria, who use study product at least once and have data from at least one post baseline QoL questionnaire to support at least one of the secondary endpoint assessments (i.e. have a non-missing response in the ‘Western Ontario and McMaster University Osteoarthritis Index’ or ‘EQ-5D-5L Quality of Life Questionnaire’ eDiary pages). The mITT population will be used for all efficacy analysis.”

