## **7.4.7 Efficacy Variables**

### **7.4.7.1 Primary Efficacy Variable**

For primary analysis, average minutes of MVPA on Day 7 will be calculated over all non-missing days between study day 1 (product usage) through 7, inclusive and it is collected via the Actigraph device. Average minutes of MVPA on Day 14 will be calculated over all non-missing days between study day 8 through 14, inclusive. Average minutes of MVPA on Day 21 will be calculated over all non-missing days between study day 15 through 20, inclusive. Any days beyond day 20 will be excluded from all summaries and analyses and will only be present in listed data.

Average baseline MVPA is computed as:

- Average baseline MVPA = total minutes of MVPA over the baseline period / number of days with non-missing data over the baseline period.
  - Baseline period is defined in section 7.1.

Average MVPA for each 7-day period is calculated as:

- Average MVPA for 7-day period = total minutes of MVPA over the period / number of days with non missing data over the period.
  - If every day within the 7 – day period has non missing data, then the Average MVPA for 7- day period will be computed as: total minutes of MVPA over the period / 7.

Change from baseline is calculated as:

- Average MVPA for 7-day period - Average baseline MVPA.

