**Change from baseline in self-reported pain intensity, assessed through Numeric Rating Scale (NRS) (daily assessment).**

Self-reported pain intensity is recorded on the 'Numeric Rating Scale' eDiary page at each scheduled timepoint.

Baseline is the value collected on Day 0, as described in section 7.1.

Change from baseline is calculated as:

- NRS score at Scheduled Timepoint – NRS baseline score (Day 0)

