### 8.2 Specific Methods for Efficacy Analyses

For the primary and secondary endpoints where the data is collected through the activity tracker, only subjects who meet the minimum wear threshold will be included in the analysis. This is defined as a minimum of 3 valid days during the baseline period and a minimum of 3 valid days within each post-baseline 7-day period, where a valid day is defined as a minimum wear of 20 hours per day.

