### 10.6 Efficacy Results

#### 10.6.1 Primary Efficacy Analysis

Table **CCI** summarizes change from baseline in the average minutes of MVPA at day 7, day 14 and day 21 by summary statistics by timepoint along with the analysis results specified in section 8.2.2 for the mITT.

Figure **CCI** presents MVPA over time for the mITT.

Listing **CCI** presents all MVPA data for the mITT.

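### SAP 6.1 requires a post-baseline WOMAC or EQ-5D-5L response for every efficacy analysis, including tracker, NRS, KSS and time-to-relief endpoints that do not use those questionnaires

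*SAP*

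**What the plan says.** **The set.** Under SAP 6.1, mITT members must be eligible, have used the product at least once, and "have data from at least one post baseline QoL questionnaire to support at least one of the secondary endpoint assessments". A bracketed clause limits this to a non-missing response on the WOMAC or EQ-5D-5L diary pages. The section ends: "The mITT population will be used for all efficacy analysis".

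**Where it is used.** SAP 10.6.1 gives the primary MVPA table "along with the analysis results specified in section 8.2.2 for the mITT". SAP 10.6.2 puts steps, sedentary ratio, gait, morning activity, NRS and KSS on the same set, and SAP 10.6.3 does so for time to meaningful pain relief.

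**Where the data come from.** For MVPA, SAP 7.4.7.1 says "it is collected via the Actigraph device". For pain, SAP 7.4.7.2 says "Self-reported pain intensity is recorded on the 'Numeric Rating Scale' eDiary page at each scheduled timepoint". KSS also has its own diary page. Time to relief (SAP 7.4.7.3) is built from the product-use diary page and, for censoring, the study termination page.

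**A separate tracker rule.** SAP 8.2 says that for tracker endpoints "only subjects who meet the minimum wear threshold will be included in the analysis". The threshold is at least three days with 20 hours of wear at baseline, and at least three such days in each post-baseline week.

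**The protocol.** Section 13.2 says "QoL and ePRO data will be summarized using the mITT population only" and names no population for tracker data. Section 10.2 counts NRS and the sleep/alertness questionnaires among the QoL tools.

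**The declared change.** SAP 3.5 prints the old and new definitions and introduces the change with: "This has been updated in the SAP to include that subjects must meet the inclusion/exclusion criteria".

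**The concern.** An analysis set should exclude subjects only for reasons connected with eligibility, exposure or the measurement being analysed. Here, entry to the primary analysis depends on whether a subject filled in a different instrument after treatment began. Protocol section 9 lets subjects who miss questionnaires stay in the study, but the SAP can then discard their valid activity, pain or pain-relief data. The SAP names no other efficacy set and no sensitivity analysis without the condition.

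Two things are at stake. One is a modest loss of precision. The other is selection towards subjects who engage with the diary, in a single-arm study that has no comparator in which the same selection would operate. The filter also fits poorly with SAP 8.2.5.1, which relies on all observed data to inform what is missing.

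**Working it through.** **Step 1. Who is lost only to the questionnaire condition?** WOMAC and EQ-5D-5L fall due after baseline on Days 1, 7, 14 and 21 (protocol Table 1-1). One response on any of those days keeps the subject in. In every row below the subject is eligible and has at least one product-use entry of yes, because SAP 7.1 derives first use from that diary page.

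| Analysis | Data needed | Lost only to the condition |
|---|---|---|
| MVPA and tracker secondaries | Actigraph, SAP 8.2 wear rule | Three or more valid days at baseline and in each of the three weeks, but no WOMAC or EQ-5D-5L entry on any of the four days |
| NRS (SAP 8.2.3: Days 7, 14, 21) | NRS page | NRS entered on Day 7, 14 or 21, but no WOMAC or EQ-5D-5L entry on any of the four days |
| KSS (same days) | KSS page | As for NRS, with KSS |
| Time to relief | Product-use and termination pages | Any event or censoring time, but no WOMAC or EQ-5D-5L entry |

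The first row is demanding: full wear across the study together with complete neglect of two questionnaires. In the NRS and KSS rows, the subject opens the diary on a scheduled day, answers one page and skips the others. The last row needs no wear and no Day 7 data, so the condition acts there most freely.

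**Step 2. One subject followed through.** Suppose a subject uses the gel, misses the Day 1 questionnaires, reports before Day 7 that the gel was not used because the pain had gone, and skips the exit questionnaires.

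- MVPA: no wear in Weeks 2 and 3, so SAP 8.2 as written already excludes this subject.
- NRS: scores before Day 7 do not enter the model, so nothing is lost.
- Time to relief: SAP 7.4.7.3 counts this as an event, and the mITT removes it.

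If n subjects use the product, k reach relief by a given day and there is no earlier censoring, dropping one event changes the curve by k/n − (k−1)/(n−1) = (n−k)/[n(n−1)], which is at most 1/n. With n = 195 (assuming every enrolled subject uses the product), that is at most 1/195 = 0.5 percentage points per dropped event.

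**Step 3. How sensitive is power to the analysed number?** Inputs from protocol 13.1 and SAP 3.2.1: effect size 0.25, two-sided alpha 0.05, power 80%, 147 completers, 25% dropout.

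Reproducing the plan's figure: the normal approximation gives [(1.96 + 0.84)/0.25]² ≈ 126, and the noncentral t gives 128. Dividing by the minimum asymptotic efficiency of the Wilcoxon test, 128/0.864 = 148, against 147 stated. With dropout, 147/0.75 = 196, against 195 stated. Both agree to within one.

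Using an effective size of 0.864 × N and noncentrality 0.25 × √(0.864 N):

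| Assumed loss | N | Power |
|---|---|---|
| 0% | 147 | 79.8% |
| 2% | 144 | 79.0% |
| 5% | 140 | 77.9% |
| 10% | 132 | 75.4% |

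The loss percentages are assumptions. The table shows how power responds to N and does not estimate the loss.

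**Step 4. What changed from the protocol?** Setting protocol 13.2 beside SAP 6.1 gives three differences: eligibility is added, the set is extended from QoL and ePRO data to all efficacy, and the qualifying pages are limited to WOMAC and EQ-5D-5L. The lead-in in SAP 3.5 names only the first.

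**The case against.** The case for leaving the text alone has real substance.

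- **Early leavers.** A reader might infer that the condition costs the primary and NRS analyses the data of subjects who leave before Day 7. It does not. The wear rule already excludes them from tracker analyses, and the NRS model starts at Day 7. Week 1 tracker data could count only if the wear rule were applied week by week, which is not what SAP 8.2 says.
- **A count.** A reader might assume each entry is missed independently with probability 0.3 to 0.5 and obtain 0.3⁴ = 0.8% to 0.5⁴ = 6.3%, or 1 to 9 of 147. The documents support neither the rates nor the independence. The base is also wrong: the 147 are completers, and protocol 5.3 defines a completer as having done every assessment, so none of them can lack all the questionnaires.
- **NRS.** A reader might think the SAP newly placed NRS on the mITT. Protocol 13.2 already did so for ePRO data. Only the narrowing of the qualifying pages is new.
- **Disclosure.** A reader might call the change undeclared. SAP 3.5 prints the new definition in full. The gap is that its explanation names one of three differences.
- **Safeguards.** The investigator reviews the diary at Days 7, 14 and 21 (protocol 9.3), and subjects who stop early are prompted to complete the questionnaires (protocol 9.2.2). A subject with no product-use entry of yes would be excluded under any sensible set.

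All of this stands, and it limits the size of the problem. None of it gives a reason for the condition: the wear rule already secures the validity of MVPA, and an NRS, KSS or product-use entry needs no support from WOMAC or EQ-5D-5L.

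**Conclusion.** The point holds as a defect in the definition of the analysis set, probably with a small effect. A post-treatment condition unrelated to the measurement governs the primary endpoint, the tracker secondaries, NRS, KSS and time to relief. For MVPA the number lost may be near zero if SAP 8.2 is read as requiring wear in every week. For NRS and KSS it is limited to subjects who answer those scales on the analysis days but never complete WOMAC or EQ-5D-5L. For time to relief the condition can remove genuine early events, or censored follow-up, with nothing else standing in the way. The direction of any bias there depends on the mix of the two.

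The documents give no rate, so no count is claimed. Even an assumed 10% loss would lower power by only about 4.4 points (79.8% to 75.4%), under the plan's effect size and the conservative Wilcoxon efficiency. The argument for acting is that the loss is selective, serves no purpose and is cheap to avoid.

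**What to change.** Define the efficacy set by endpoint in SAP 6.1:

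- Tracker endpoints: eligible, product used at least once, and the SAP 8.2 wear criteria met.
- NRS and KSS: eligible, product used, and at least one post-baseline value of that scale.
- Time to meaningful pain relief: eligible and product used.
- WOMAC and EQ-5D-5L: keep the present questionnaire condition.

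Align SAP 10.6.1 to 10.6.3 with these sets. In SAP 3.5, name the extension of the mITT to tracker data and the narrowing of the qualifying questionnaires as departures from the protocol, and state how the revised sets deal with each. Report, by endpoint, how many subjects only the questionnaire condition would have excluded, so that the size of the issue becomes known.

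The cost is SAP wording and one extra population flag. The downside is that denominators will differ slightly between endpoints, which a line in each table can explain.

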### 6.2 Subgroup Definitions

No subgroup analysis is planned.

## 7. Definition of Time Points and Analysis Variables

### 7.1 Definition of Time Points

Visits are labelled in all TLF outputs as they were entered into the eCRF/eDiary without re-labelling. External data will be analysed according to the study day calculated.

**Table 3: Study Visits**

Scheduled Visit	Scheduled Visit Label	Scheduled Study Day
Screening*	Screening	-7
Day -6	Day -6	-6
...	...	...
Day -1	Day -1	-1
Day 0*	Day 0	0

Scheduled Visit	Scheduled Visit Label	Scheduled Study Day
Day 1	Day 1	1
Day 2	Day 2	2
Day 3	Day 3	3
Day 4	Day 4	4
Day 5	Day 5	5
...	...	...
Day 21*	Day 21	21

\*Indicates mandatory site visit.

### Date of First Study Treatment Administration

Date of first study treatment administration is derived as:

- (The earliest recorded date where the answer to the question “Did you use yesterday the Voltaren Gel as per label and leaflet instructions?” is “Yes” on the ‘Study Product Use’ eDiary page) - 1.

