### Pre-Treatment Adverse Events

Pre-treatment AEs are defined as AEs that started during the pre-treatment period (date of informed consent up to the date/time of first study treatment administration).

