## **Treatment-Emergent Adverse Events (TEAEs)**

A treatment-emergent adverse event (TEAE) is defined as an AE that started on or after the date of the first study treatment administration and is derived using start/onset and stop dates only.

Missing AE dates are handled according to the same rules as specified for concomitant medications in Section 7.2.

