## 10.7 Safety Results

### 10.7.1 Adverse Events

#### 10.7.1.1 Brief Summary of Adverse Events

An Overview of AEs including but not limited to

- the number of subjects with at least one AE;
- the number of subjects with at least one pre-treatment AE;
- the number of subjects with at least one TEAE;
- the number of subjects with at least one Serious TEAE;
- the number of subjects who permanently discontinued Study Treatment due to a TEAE;
- the number of subjects with a TEAE related to study treatment;
- the number of subjects who had a TEAE with outcome of death
- the worst severity of any TEAE experienced by each subject with at least one TEAE

is summarized by treatment and overall, for the SAF in Table CCI [REDACTED]

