#### 10.7.1.3 Listing of Adverse Events

Listing **CCI** presents all Adverse Event data (raw, derived, and coded), for the SAF.

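### Safety-population membership and treatment-emergent status rest only on a diary 'Yes' to on-label use, which is narrower than the protocol's any-use rule and has no fallback; the likely effect is small

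*SAP*

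**What the plan says.** Protocol 13.2 defines the population by use alone: "The safety population will include all subjects who use study product at least once". It sets no condition on label compliance or on a diary entry.

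SAP 6.1 repeats that and then makes it operational. It admits subjects "who use study product at least once i.e. if a subject has a date of first study treatment administration", as derived in SAP 7.1. SAP 7.1 gives that date one source: the earliest eDiary date with 'Yes' to "Did you use yesterday the Voltaren Gel as per label and leaflet instructions", minus one day. The date of last administration, in the same section, comes instead from the Study Termination eCRF page.

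SAP 7.4.8 hangs event classification on the same date. Pre-treatment events run from "date of informed consent up to the date/time of first study treatment administration"; a treatment-emergent event is "an AE that started on or after the date of the first study treatment administration". All adverse-event tables in SAP 10.7.1 are for the safety population. The overview there counts "the number of subjects with at least one pre-treatment AE", and the listing "presents all Adverse Event data (raw, derived, and coded), for the SAF".

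SAP 8.2.5.1 replaces no missing data except adverse-event dates. SAP 7.2.2 imputes those dates relative to first administration, without saying what happens when that anchor is itself missing. SAP 3.5 declares one change from the protocol: "This has been updated in the SAP to include that subjects must meet the inclusion/exclusion criteria to be included in the mITT".

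**The concern.** Whether an event counts in the safety tables should depend on whether the gel was used. Here it depends on whether a diary page was completed, and on how the subject answered a question that asks about use and label compliance together.

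There are two consequences. A user with no 'Yes' has no first-dose date, so is outside the safety population and outside every adverse-event table and the listing, even if the eCRF holds a date of last application. A user whose first 'Yes' comes late has events in the gap classed as pre-treatment; these leave the treatment-emergent, serious treatment-emergent and related treatment-emergent tables.

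The missed-diary route is documented: Protocol section 9 lets subjects continue after missed daily questionnaires. Under Protocol 9.2.3 the study ends the day after the last treatment if that falls before Day 21, so a one-day user may have a single entry in which to record use. Monitoring adverse events is a stated objective, and Protocol Table 11-2 classes dermatitis, rash and pruritus as common. A subject who stops at once because of such a reaction is the one most exposed to this rule.

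**Working it through.** **Text check.** The definitions line up as follows.

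| Step | Rule | Place |
|---|---|---|
| Protocol population | any use, at least once | Protocol 13.2 |
| SAP population | a first-dose date exists | SAP 6.1 |
| First-dose date | earliest diary 'Yes' to on-label use, minus 1 day | SAP 7.1 |
| If no 'Yes' exists | nothing stated | SAP 7.1, 7.2.2, 8.2.5.1 |
| Declared as a change | no | SAP 3.5 |

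A missing or 'No' answer can only make the derived date late or absent, so this mechanism moves events out of the treatment-emergent tables and never into them.

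**Size.** The plan states no figure to reproduce, and no rate of missing or 'No' answers. The following is an illustration. Assumptions: 195 users (the planned enrolment), 21 days of use, 10 users with one event each, and each day of use lacking a 'Yes' independently with probability p from 0.05 to 0.20.

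- Starting rate: 10/195 = 5.13%.
- Users whose derived date is at least one day late: 195p = 9.75 to 39.
- Expected subject-days in the gap: 195 × p/(1−p) = 10.26 to 48.75. Divided by 195 × 21 = 4,095, this is 0.251% to 1.190%.

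*Events relabelled as pre-treatment, of 10:*

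| Onset pattern | Formula | Relabelled | Treatment-emergent rate, (10−x)/195 |
|---|---|---|---|
| Even over 21 days | 10 × gap fraction | 0.025 to 0.119 | 5.12% to 5.07% |
| Half on first day of use | 5p + 5 × gap fraction | 0.263 to 1.06 | 4.99% to 4.58% |
| All on first day of use | 10p | 0.5 to 2.0 | 4.87% to 4.10% |

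*Users with no 'Yes' at all.* With d days of use the probability is p^d. Per 10 such users:

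- d = 1: 0.5 to 2.0
- d = 2: 0.025 to 0.40
- d = 3: 0.00125 to 0.08
- d = 7: about 0

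If 2 of the 10 users with an event stop after one day, 2p = 0.1 to 0.4 of them leave the population. The rate becomes (10−x)/(195−x) = 5.08% to 4.93%.

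Loss from the population is therefore confined almost entirely to users of one or two days. Late dating is more common but short. Independence may understate the problem if people who stop after a reaction are also the ones who skip the diary.

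**The case against.** The strongest reply is that SAP 6.1 repeats the protocol sentence and only adds a data rule, so nothing was changed and nothing needed declaring. That may well have been the intention. The wording is still narrower, and the wording is what gets programmed. Dataset specifications sit in a separate document (SAP 5.2), so the absence of a fallback is established only for the protocol and SAP.

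Second, the plan has safeguards. Subjects who stop early are prompted to complete all relevant questionnaires (Protocol 7.7, 9.2.2). Those taken off treatment should stay for the remaining assessments (8.1). Diaries are reviewed at Days 7, 14 and 21 (9.3), and product use is monitored throughout (13.3.6.1). These make a high p less plausible. They do not supply a date when the entry is missing.

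Third, some affected events remain visible. For subjects inside the population, relabelled events stay in the overview and the listing. For the Enrolled Population, the SAP lists concomitant medications and procedures, major deviations and the reason for exclusion from the safety population. Serious-event reporting under Protocol 11.3.2 does not use this date.

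A reader might go further and infer that anyone who used the gel but not per label answers 'No' and is dropped. The documents do not show this. The diary page and its full list of reasons are not included, and SAP 7.4.7.3 names only the reason it needs. That route is possible but inferred.

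**Conclusion.** The point holds. The SAP's rule is narrower than the protocol's, rests on one diary answer, and has no stated fallback. A real user can be left out of all adverse-event tables and the listing, and an early on-treatment event can be labelled pre-treatment.

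The likely effect is small. It falls mainly on very short users and on events in the first days, and the tables are descriptive in a single-arm study. Under the assumed range of p, even onset moves the rate by at most 0.06 percentage points (5.13% to 5.07%). Only the corner with p = 20% and every event starting on the first day of use brings it to 4.1%. The values of p, the number of events, the onset pattern and the number of one-day users are all assumptions.

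A reader might infer that the trial's safety results will be materially understated; neither the documents nor this range supports that. The change is worth making because it is cheap and the rule as written gives the wrong answer for an identifiable kind of subject.

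**What to change.** 1. Define the safety population by any recorded evidence of use: a diary 'Yes', an eCRF date of last application, or another record that states use.
2. Keep the diary-derived first-dose date by default. Only where it is missing, or where scheduled diary entries between dispensing and the first 'Yes' are missing, class events starting after dispensing as treatment-emergent. This is a conservative rule by analogy with the worst-case principle in SAP 7.2.2, which itself covers event dates rather than the first-dose date. Applying it to every subject would be too broad: it would create a second marker of first use and could make Day 0 events before dispensing treatment-emergent in fully compliant subjects.
3. Do not use the last-application date as a first dose. Where there is no diary date, show exposure, compliance and time to pain relief as missing.
4. List adverse events for all subjects who were dispensed product.
5. State the rule in SAP 3.5.

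Separately, reconcile SAP 7.4.4. It equates stopping before first administration with an end day below 1, but SAP 7.1 counts study days from the baseline visit. After a late first 'Yes', a drug given on Day 1 for an event in the gap is concomitant by the day rule, while the event it treats is pre-treatment.

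Cost: SAP wording, a change to one event flag and a wider population for one listing. Diary answers, baseline visit date, last-application date and event start dates are already collected. Whether accountability or dosing-error records state use is not shown, so they count only where they do. The SAP history shows that version 2.0 already carries the data-review updates, so a further version is needed; the documents do not show whether the database has been locked. A few true pre-treatment events may be counted as treatment-emergent, which is the cautious direction for safety.
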